## 5. Background for Proposed Trial

In recent years, the treatment of intracranial aneurysms has shifted from a primarily surgical paradigm to one of endovascular management. The International Subarachnoid Aneurysm Trial (ISAT), published in 2002, demonstrated improved mortality and dependency rates at one year in those undergoing endovascular coil embolization to those undergoing clipping. However, anatomic challenges and technological limitations continue to limit the application of endovascular techniques for many aneurysms.

In particular, wide-neck aneurysms have long been a challenge for endovascular techniques. As a result vascular remodeling (e.g., balloon or stent-assisted) embolic coiling has become increasingly common. Additionally, recent success has also been encountered with the use of flow diversion technologies. However, limitations continue to exist, especially in branching locations for wide-neck aneurysms, which typically occur in the middle cerebral artery and basilar artery. Flow diversion is not currently approved for these locations. Recent published reports indicate that when flow diversion is used off-label in such locations, the results are dismal. Therefore, the Barrel® VRD was developed specifically to address these challenging locations. Designed with an expanding central portion of the device, the Barrel® VRD is intended to protect both parent vessels for bifurcating and branching aneurysms.

The lack of technologies specifically designed to address these aneurysm subtypes is reflected in lower successful embolization rates reported in the literature. There is a paucity of literature available that specifically evaluates only branching/bifurcating aneurysms. However, in those studies that do provide evaluation, it is evident that this aneurysm subtype presents a substantially more challenging lesion with lower than typical success rates.

In an early publication, Bavinski, et al. evaluated their experience in treating 45 basilar tip aneurysms over a six year period. They reported that in wide-necked basilar aneurysms complete occlusion was achieved only 15% of the time. This result was comparable to a number of other contemporaneous series. For instance, McDougall, et al. reported a 21% complete occlusion rate on follow up angiography for 19 basilar tip aneurysms and Raymond, et al. demonstrated a 19% complete occlusion rate for wide-neck basilar tip aneurysms, versus 67% complete occlusion in small neck basilar tip aneurysms. While these early studies pre-date many modern adjunctive technologies, they

clearly illustrate the challenges associated with wide-neck branching pathologies.

More recent data demonstrates progress, but there are continued limitations when dealing with branching wide-neck aneurysms. A recent study by Lodi, et al. evaluating stent-assisted coiling in 87 aneurysms, of which 50 were located at branching (as opposed to side wall) locations, demonstrated a 31% complete occlusion rate. This study used modern stent-assisted technology in all cases and included a large number of ICA sidewall locations, that are known to experience better rates of occlusion, and yet still achieved a very low rate of complete occlusion, likely secondary to the inclusion of branching wide-neck aneurysms. It should also be noted that these results, as well as all the currently published series regarding this aneurysm subtype, are self reported and not adjudicated by a core lab. A fact that is well documented to result in higher occlusion rates than core lab adjudicated series.

There are three very recent studies that specifically address bifurcating wide-neck basilar or MCA aneurysms. Unfortunately, all of these studies are retrospective and present self-reported outcomes. The literature has repeatedly demonstrated that retrospective non-adjudicated studies consistently over-estimate treatment benefit and underestimate complications, however, these are the best data available. These data strongly demonstrate the continued limitations of current technology. Fargen, et al. reported their results treating 45 wide-neck bifurcating aneurysms with the Y-stenting technique. Despite experiencing an initial procedural/peri-procedural complication rate of 22.2%, they achieved an initial self-reported complete occlusion rate of 43%. Unfortunately, they only obtained follow-up imaging in 30 of their patients, preventing a reasonable assessment of their follow-up occlusion rates. Despite there being a high likelihood of selection bias towards the successfully treated aneurysms in the patients with follow-up, they demonstrated a self-reported 56% complete occlusion rate on follow up (when counting the two deaths as failures). Overall, for their entire cohort they demonstrated successful complete occlusion on last known angiogram in 40% of patients. Spiotta, et al. likewise reported their retrospective non-adjudicated results treating 19 patients with bifurcating aneurysms with stent-assisted coiling. They experienced a 32% complication rate and achieved an initial self-reported complete occlusion rate of 26%. On follow-up imaging they self-reported a 53% complete occlusion rate (without re-treatment), and for their entire cohort they demonstrated 47% of patients having complete occlusion on last known angiogram. The final series evaluating stent-assisted embolization of wide-neck bifurcating basilar aneurysms is a very recent publication by Zhang, et al. They report their results with treating 23 wide-necked basilar aneurysms. In this study, the authors report a self-adjudicated complete occlusion rate of 39.1%. Mean angiographic follow-up at 13.5 months was reported for 16 patients. Within that selected cohort they experienced a self-reported complete occlusion rate of 62%, with a self-reported all patients' complete occlusion rate of 43%.

Despite substantial progress over the past decade, endovascular treatment of bifurcating aneurysms remains a significant challenge. Despite the lack of independent adjudication, a composite analysis (all complete occlusions divided by the total number of patients), of the above reviewed modern studies demonstrate only a 42% overall complete occlusion rate at follow-up. The mean and standard deviation of all three studies (treating each study as a single entity) is 43% and 3.5%, respectively. Again, it is worth noting that all of these studies were retrospective and un-adjudicated, significant contrasts to the proposed prospective adjudicated study, and a methodology well demonstrated to overestimate successful occlusion rates and underestimate complication rates. However, these data are the best available for this disease state.

## 6. Statistical Considerations and Analysis

The primary efficacy endpoint to be evaluated in this study is the outcome of treated aneurysms from study subjects achieving Raymond Grade I (100% occlusion) at 12 months  $\pm$  8 weeks in the absence of retreatment, parent artery stenosis (> 50%), or target aneurysm rupture. The rate of the primary efficacy endpoint will be formally compared to a historical control, which is derived using a meta-analysis of the three very recent studies that specifically address bifurcating wide-neck basilar or MCA aneurysms (Fargen et al, 2013; Spiotta et al, 2011; and Zhang et al, 2014) as summarized in the Table 6-1. The study will be conducted at up to 28 centers and will enroll up to 159 subjects to ensure treatment/attempted treatment of 119 subjects (107 evaluable assuming a 10% loss to follow-up rate).

### 6.1 Determination of Historical Control

The BARREL Study is designed as a single-arm trial, which will be compared against a historical control derived from a meta-analysis of the rate of primary efficacy endpoint. i.e. outcome of treated aneurysms from study subjects achieving Raymond Grade I (100% occlusion) at 12 months  $\pm$  8 weeks in the absence of retreatment, parent artery stenosis (> 50%), or target aneurysm rupture. A follow-up target of 12 months was chosen specifically because it matches the mean follow-up of the meta-analysis. The Table 6-1 summarizes types of aneurysms, demographic information, and clinical outcomes of three very recent studies that specifically address wide-necked basilar and MCA aneurysms. Information about these studies is summarized in Section 5, “Background for Proposed Trial”. An overall estimate of the rate of the primary efficacy endpoint derived from the meta-analysis of these three trials is 42.5% with the 95% confidence interval of (31.90%, 53.06%). This overall estimate provides the basis for deriving the historical control.

**Table 6-1 Meta-Analysis for Historical Control**

Study	Number of Aneurysms in the Trial	Number of Bifurcation Aneurysms in the Trial	Number of Wide-Necked Aneurysms in the Trial	Mean Age	Number of Women	Follow-up Time (Months)	Number with Angiographic Follow-up	Number of Raymond Grade I at Follow-up	% of Raymond Grade I of those Followed-up	% of Raymond Grade I of Cohort
Fargen 2013	45	45 (100%)	45 (100%)	57.9	31 (69%)	9.8	30	18	56%	40% (18/45)
Spiotta 2011	19	19 (100%)	19 (100%)	57.4	14 (74%)	16	17	9	52.90%	47% (9/19)
Zhang 2014	23	23 (100%)	23 (100%)	51.2	12 (51%)	13.5	16	10	62.5%	43% (10/23)
Total	87	87 (100%)	87 (100%)		57 (66%)	12.1	63	37	57.1%	42.5% (37/87)

The estimation of the rate of the primary endpoint derived from the three referenced studies, using the weighted proportion and its standard error (SE), was calculated using the following formula:

$$\hat{P} = \frac{\sum_i W_i p_i}{\sum_i W_i}, \text{ where } \hat{P} \text{ is the combined rate of complete occlusion;}$$

$p_i$  is the rate of complete occlusion in each referenced study;

$$W_i = \frac{1}{S_i^2}; S_i^2 = \frac{p_i(1-p_i)}{n_i}; \quad \text{where } n_i \text{ is the sample size of each reviewed study;}$$

$$SE(\hat{P}) = \sqrt{(\sum W_i)^{-1}}$$

and the 95% confidence interval (CI) is  $\hat{P} \pm 1.96 * SE(\hat{P})$ .

## 6.2 Primary Analysis

The goal of the primary analysis will be to demonstrate that the Barrel® VRD device performs better than the combined historical control treatments for complete occlusion rate at 12 months. The hypothesis to be tested is:

$$H_0: \pi_B = \text{HC} \text{ versus } H_A: \pi_B > \text{HC}$$

Where  $\pi_B$  is the proportion of successful outcomes for the Barrel® VRD device and HC is the combined overall historical control success rate. Success is defined as a subject with a Raymond Grade of 1 (100% occlusion) at 12 months  $\pm$  8 weeks in the absence of retreatment, parent artery stenosis (> 50%), or target aneurysm rupture. This hypothesis will be tested using an exact one sample binomial test at ( $\alpha = 0.025$ ). Exact 95% confidence intervals will be constructed.

The meta-analysis analysis mentioned above provides an overall estimate for historical control success rate of 42.48% with a 95% confidence interval of (31.90%, 53.06%).

Although the meta-analysis provides the basis for deriving a historical control success rate, it does not allow exact comparison due to the author-evaluated Raymond Grades used in the studies versus the proposed core laboratory grade reporting. Moreover, the reported rates in the published literature do not take into account patients lost to follow-up in their final calculation of occlusion rates. Conversely, the Barrel study employs a more stringent intent-to-treat (ITT) methodology that treats those patients lost to follow up as treatment failures. A review of the literature shows that onsite angiographic evaluators report 20 to 60% higher Raymond Grade success rates than those reported by core laboratories. Rezek et al. (2013) states “Core laboratories tend to report higher rates of unfavorable outcomes compared with self-reporting centers. Indeed, the rate of unfavorable outcomes was 43.6% greater in core laboratories compared with noncore laboratory studies.” McDougall CG et al. (2014) states, “in 36% of cases, the local investigators reported a better degree of occlusion than did the core laboratory.”

Unfortunately only one paper, Rezek et al. (2014), provided sufficient detail of the operator and core laboratory

results, in a population that is representative of the patient population that is proposed in the protocol, to allow statistical analysis of the difference.

An analysis of this data provided an adjustment of 36% between the operator results and the core laboratory results. This difference was consistent with the other published results. After adjustment, the estimated historical success rate for core lab results is 28%. The corresponding adjusted confidence interval is (23%, 33%).

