### 6.3 Sample Size Calculation

In actuality, the real objective of this study is to demonstrate that the Barrel® VRD is comparable to historical controls. Therefore the historical success rate of 28% was selected as the historical control value. The Barrel® VRD will be considered successful if its lower 95% confidence limit is greater than 28%.

Table 6-2 presents the sample size necessary to have an 80% power with a significance level of 2.5% for rejecting the null hypothesis in favor of the alternative when the true success rate for the Barrel® VRD is as specified. The hypotheses to be tested are:

$$H_0: \pi_B = 28\% \text{ versus } H_A: \pi_B > 28\%$$

Where  $\pi_B$  is the proportion of successful outcomes for the Barrel® VRD device.

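### Section 6.2 aims at superiority to the historical treatments, but the 2.5% error rate and 80% power hold only for exceeding a fixed 28%, because the control's sampling error is left out of the test

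*Protocol*

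**What the plan says.** Section 6.2 of the protocol gives the goal of the primary analysis as showing that the device "performs better than the combined historical control treatments for complete occlusion rate at 12 months". The null is that the Barrel rate equals HC, where "HC is the combined overall historical control success rate". On the method it says: "This hypothesis will be tested using an exact one sample binomial test", at alpha 0.025, with exact 95% confidence intervals.

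The control rate is presented as an estimate. Sections 6.1 and 6.2 give 42.48% from 87 aneurysms in three published series, with a 95% interval of 31.90% to 53.06%. Section 6.2 then applies a 36% operator-to-core-laboratory adjustment and arrives at 28%, with an adjusted interval of 23% to 33%.

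Section 6.3 continues: "Therefore the historical success rate of 28% was selected as the historical control value". It writes the null as a Barrel rate of 28%, declares success if the lower 95% limit exceeds 28%, and sizes the trial for "80% power with a significance level of 2.5% for rejecting the null hypothesis in favor of the alternative". It also describes the real objective as comparability with historical controls. The control interval enters neither the test, nor the pass rule, nor the sample size.

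**The concern.** The hypothesis in Section 6.2 compares the device with treatments whose true success rate is unknown. The test compares it with a number. Both statements carry the same alpha of 0.025, but a one-sample binomial test protects only the second.

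This matters for a narrow pass. Read against the Section 6.2 goal, 40 successes of 107 would support a claim of beating existing treatments at one-sided 0.025. Part of that apparent margin could be sampling error in a control rate drawn from three small retrospective series. The point stands even if 28% is the right point estimate, and it does not depend on whether the reader adjustment is correct.

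**Working it through.** **Inputs.** Evaluable N = 107 (Section 6); expected rate 41%, control value 28%, alpha 0.025 (Sections 6.2 and 6.3); adjusted interval 23% to 33% (Section 6.2); successes 18/45, 9/19 and 10/23 (Table 6-1).

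**1. Reproduce the plan's figures.** Take the smallest N at which the exact rule P(X ≥ r | 0.28) ≤ 0.025 has at least 80% power. This returns every entry of Table 6-2, including 107 at 41%. Then 107/0.9 = 118.9, so 119 treated. At N = 107:
- r = 39: lower exact 95% limit 27.4%, P(X ≥ 39 | 0.28) = 3.5%. Fails.
- r = 40: lower limit 28.2%, P(X ≥ 40 | 0.28) = 2.2%. Passes.
- Power: P(X ≥ 40 | 0.41) = 80.4%.

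Against a fixed 28%, the stated alpha and power are met.

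**2. Standard error of the control.**
- From the printed adjusted interval: (33 − 23)/(2 × 1.96) = 2.55 points.
- From the pooled analysis: the Section 6.1 weights n/[p(1 − p)] are 187.5, 76.2 and 93.6, sum 357.3. The pooled rate is 42.48% and the SE is 1/√357.3 = 5.29 points. Scaled in proportion to 28%: 5.29 × 28/42.48 = 3.49 points. The protocol does not print this SE; it is an assumption of this review. Starting from the printed unadjusted interval instead gives (53.06 − 31.90)/(2 × 1.96) = 5.40, scaled to 3.56.

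**3. Averaged false-positive rate for the comparative claim.** Set Barrel's true rate equal to the controls' true rate θ, let θ be normal around 28% with the SE above, and average P(X ≥ 40 | 107, θ).

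| SE of control | Averaged pass rate |
|---|---|
| 0 (fixed 28%) | 2.2% |
| 2.55 points (printed interval) | 4.1% |
| 3.49 points (rescaled) | 5.8% |
| 3.56 points (rescaled from printed interval) | 5.9% |

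With all 119 subjects evaluable (cut-off 44), the fixed-28% alpha is 2.1%, and the averaged rates are 4.2% for SE 2.55 and about 6.0% for SE 3.49.

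**4. Fixed true control rates at the ends of the printed interval.** A device exactly equal to controls passes with probability P(X ≥ 40 | 0.23) = 0.06% or P(X ≥ 40 | 0.33) = 19.4%.

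**5. A narrow pass under a comparison that carries the control SE.** Use z = (p − 0.28)/√[p(1 − p)/107 + SE²], with p = 40/107 = 0.3738.
- SE 2.55: z = 0.0938/0.0533 = 1.76, one-sided p = 0.039.
- SE 3.49: z = 0.0938/0.0583 = 1.61, one-sided p = 0.054.

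**6. Successes needed for p ≤ 0.025 on that comparison.**
- SE 2.55: 41 gives p = 0.027 and 42 gives 0.018, so 42 are needed. P(X ≥ 42 | 0.41) = 67.8%.
- SE 3.49: 42 gives p = 0.028 and 43 gives 0.019, so 43 are needed. P(X ≥ 43 | 0.41) = 60.4%.

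**The case against.** The strongest reply is that Section 6.3 assigns HC the value 28%, writes the null with that number and sets the pass rule against it. A fixed performance goal is a normal single-arm design, the literature is already published, and the threshold does not vary. On that reading nothing is mis-sized. This stands: the test is valid for the null in Section 6.3.

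A reader might infer that the trial's type I error is really 6% and not 2.5%. The documents do not support that. The 6% needs an SE the protocol does not print, while the interval it does print gives about 4%. Both are averages over uncertainty in the control, not the size of the fixed test, so they should not be set beside 2.5% as the same quantity. Likewise the 19% at a control rate of 33% must be read with the 0.06% at 23%.

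The protocol also tempers the comparison. Section 6.2 concedes that the literature does not permit an exact comparison, and Section 6.3 speaks of comparability. But the superiority goal remains in the section that defines the primary analysis, under the same alpha, and Section 6.3 still labels 28% a historical control value. The mismatch between claim and test therefore remains.

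**Conclusion.** The point holds as a mismatch between claim and test, not as a mis-sized test. Alpha of 2.5% (2.2% exact) and 80% power apply to exceeding a fixed 28%. They do not apply to superiority over the historical treatments. For that claim the averaged false-positive rate is about 4% on the printed adjusted interval and about 6% on the rescaled pooled SE, and a pass at 40 of 107 does not reach one-sided 0.025 on either.

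These figures assume normal error in the control rate centred on 28%, and no error in the 36% adjustment, for which the protocol gives no SE; independent error there would raise them. The practical reach is limited to what a narrow pass, 40 or 41 successes (up to 42 with the larger SE), may be said to show.

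**What to change.** In Sections 6.2 and 6.3:

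1. State the primary hypothesis as H0: π_B ≤ 28% against HA: π_B > 28%, and call 28% a fixed performance goal.
2. Say that alpha 0.025, the exact confidence interval and the 80% power refer to exceeding that goal only. Replace the superiority goal in Section 6.2 with: the device exceeds the 28% performance goal.
3. Allow a statement of superiority to historical treatments only on a prespecified supportive comparison, such as the z statistic in the working, reported with the confidence interval of the difference. Name one control SE and quote only its own figures: SE 2.55 points needs 42 of 107 with about 68% power at 41%; SE about 3.5 points needs 43 of 107 with about 60%.

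The cost is a few sentences and one calculation from figures already in the protocol. Sample size and the Section 6.3 pass rule do not change. The downside for the sponsor is that a narrow pass supports only the performance-goal claim, and that a lower power has to be stated for the comparative one.

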### 6.3 Sample Size Calculation

In actuality, the real objective of this study is to demonstrate that the Barrel® VRD is comparable to historical controls. Therefore the historical success rate of 28% was selected as the historical control value. The Barrel® VRD will be considered successful if its lower 95% confidence limit is greater than 28%.

Table 6-2 presents the sample size necessary to have an 80% power with a significance level of 2.5% for rejecting the null hypothesis in favor of the alternative when the true success rate for the Barrel® VRD is as specified. The hypotheses to be tested are:

$$H_0: \pi_B = 28\% \text{ versus } H_A: \pi_B > 28\%$$

Where  $\pi_B$  is the proportion of successful outcomes for the Barrel® VRD device.

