## 7. Objectives

The purpose of this study is to evaluate the safety and efficacy of the Reverse Medical Barrel® VRD for Adjunctive Treatment to Embolic Coils for Wide-neck, Intracranial, Bifurcating/Branching Aneurysms of Middle Cerebral and Basilar Arteries.

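### Section 6.3 gives comparability with historical controls as the real objective, but the hypotheses test superiority to 28% with no margin, so the trial cannot support a comparability claim

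*Protocol*

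**What the plan says.** Protocol 6.2 (Primary Analysis) says the aim is to show that the "device performs better than the combined historical control treatments for complete occlusion rate at 12 months". It tests equality with the historical control rate against a higher rate, by an exact one-sample binomial test at 0.025. It then adjusts the literature rate for core-laboratory reading: "After adjustment, the estimated historical success rate for core lab results is 28" per cent, and "The corresponding adjusted confidence interval is (23%, 33" per cent).

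Protocol 6.3 (Sample Size Calculation) begins with the words "In actuality, the real objective of this study is to demonstrate that the". What it then names is not superiority, and the choice of null value is made to follow from it: "VRD is comparable to historical controls. Therefore the historical success rate of 28% was selected as the historical control value". Its decision rule is that the "VRD will be considered successful if its lower 95% confidence limit is greater than 28" per cent. The hypotheses that follow are a null of 28% and an alternative above 28%. The text under Table 6-2 justifies the assumed 41% by a possible advantage of the device.

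Safety appears elsewhere. Section 7 says "The purpose of this study is to evaluate the safety and efficacy of the Reverse Medical" device, and sections 6.6 and 8.1.1 count the primary safety endpoint as met if the upper confidence bound is at most 15%. Section 8.1.1 also gives an efficacy criterion, a lower bound above 23%, which differs from the 28% in 6.3.

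**The concern.** Sections 6.2 and 6.3 name different objectives, and 6.3 presents its own as the true one. Being better than control and being comparable to control need different designs. Comparability needs a margin below the control rate and a null placed at that margin. Here the null sits on the control estimate, which makes the test one of superiority. The word introducing the 28% in 6.3 makes it follow from comparability, and it does not.

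What is at stake is the claim the trial may make. In a single-arm study against a derived historical rate, the pre-stated claim is a main safeguard against reinterpretation. With comparability on paper as the real objective, a result that misses 28% could be described as meeting it, with no margin or test behind the statement.

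A smaller point lies in the same paragraph. The success sentence is about the device, not the efficacy endpoint, and does not mention the other primary endpoint.

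**Working it through.** **Inputs.** Null rate 28% (6.2, 6.3); exact binomial test, one-sided 0.025 (6.2, 6.3); assumed true rate 41% (6.3); 107 evaluable (section 6, Table 6-2); 10% dropout (6.3); alternative efficacy criterion 23% (8.1.1). No non-inferiority or equivalence margin is given in the protocol.

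**1. Reproduce the plan's figure.** The critical count is the smallest r with P(X ≥ r | n = 107, p = 0.28) ≤ 0.025.

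- r = 39: P = 0.0354, too large; exact lower 95% limit 27.4%.
- r = 40: P = 0.0221; exact lower 95% limit 28.2%, above 28%.

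So success needs 40/107 = 37.4%. Power is P(X ≥ 40 | 107, 0.41) = 0.804. The smallest n reaching 80% power under this method is 107, and 107/0.9 = 118.9, giving 119 treated. The same method reproduces all eight entries of Table 6-2. The sample size is right for a superiority test.

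**2. Chance of success by true rate**, P(X ≥ 40 | 107, p):

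| True rate | Chance of meeting the 28% rule |
|---|---|
| 28% (equal to control) | 2.2% |
| 30% | 6.1% |
| 32% | 13.8% |
| 33% | 19.4% |
| 41% | 80.4% |

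If all 119 were evaluable, the critical count would be 44 and a true 28% would pass 2.1% of the time. The first row of the table is the type I error: the stated real objective coincides with the null hypothesis.

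**3. What a missed result would show.** Take 30/107 = 28.0%, as close to control as this sample allows. Its exact 95% interval, from the beta quantiles B(0.025; 30, 78) and B(0.975; 31, 77), is 19.8% to 37.5%. Without a margin, nothing says whether a lower limit of 19.8% is close enough to 28% to be called comparable.

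**4. The other criterion in the text.** With a null of 23% and n = 107, the critical count is 34 (lower limit 23.1%; 33 gives 22.3%). A true 28% device then passes with P(X ≥ 34 | 107, 0.28) = 22.1%. With n = 119 the count is 38 and the chance is 19.6%. Neither threshold gives useful power for a device equal to control.

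**5. The success sentence against the safety text.** Section 6.3 calls the device successful on the efficacy limit. Sections 6.6 and 8.1.1 say when the safety endpoint is met. No section of the protocol says that both are required.

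**The case against.** The best reply is that this is one stray sentence. The hypotheses in 6.2 and 6.3, the assumed advantage behind 41%, and Table 6-2 all describe superiority, so a statistician would run the right test whatever the sentence says. That stands, and it limits the point to what may be claimed. It does not remove the point, because the sentence presents itself as correcting the stated goal and is used to justify the null value.

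It is also fair that 2.2% is no discovery: any superiority test passes a device at the null value at its type I error rate. The figure only shows which question the test answers.

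Three stronger readings are tempting and not supported.

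- A reader might infer that 28% is the only threshold. Section 8.1.1 still says 23%. The revision summary records an increase from 23% to 28%, so 23% looks like a leftover, but it is in the current text.
- A reader might infer that the protocol lets a device pass while failing on safety. The success sentence stands in the sample-size section, between the efficacy control value and the efficacy hypotheses, and safety is a primary endpoint with its own criterion. What the protocol has is a loosely worded sentence and no combining rule; the latter may be in the analysis plan, which is not at hand.
- A reader might infer that the 80% is offered as power for overall success. Section 6.3 ties it to rejecting the efficacy null. Joint-power figures would need an interval method for safety (6.6 names none), a denominator, independence and an event rate. For example, with exact intervals, independence and an assumed 7% event rate, the chance of meeting both endpoints is 0.804 × 0.788 = 63% if safety uses 119 subjects (at most 10 events), but 0.804 × 0.666 = 54% if it uses 107 (at most 8). Figures that move this much with unstated choices carry no weight here.

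**Conclusion.** The point holds as a contradiction in the stated objective, worth correcting because it governs the claim. Section 6.3 says comparable, section 6.2 says better, and the test is superiority to the control estimate with no margin. A device equal to control passes 2.2% of the time with 107 evaluable subjects, or about 20% to 22% if the 23% in 8.1.1 were applied; neither supports a comparability claim. These figures assume the exact binomial test of 6.2 and independent subjects with a common success rate.

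A reader might conclude that the trial is mis-sized or wrongly tested. It is not: the calculation reproduces exactly for superiority. The success sentence is a secondary wording fault, since it names the device where it should name the efficacy endpoint.

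**What to change.** - In 6.3, replace the sentence on the real objective with one matching 6.2: the objective is to show that the complete occlusion rate exceeds the 28% performance goal.
- Add that a lower 95% limit at or below 28% supports no claim of comparability with historical controls.
- Reconcile the efficacy criterion in 8.1.1 (23%) with 6.3 (28%), so that one threshold stands throughout.
- Reword the 6.3 success sentence to say that the primary efficacy endpoint is met if the lower 95% limit exceeds 28%. Add that study success requires both this and the 15% safety criterion of 6.6 and 8.1.1.

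This costs wording in 6.3 and 8.1.1. The test, Table 6-2 and the 119 treated subjects are unchanged, and requiring both endpoints needs no alpha adjustment. The price is that the sponsor gives up a fallback claim of comparability. If comparability is really wanted, a justified margin is needed, and the hypotheses and sample size must be derived again.
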